6.2.6 ECOG Performance Status Score

The ECOG performance status score has a range from 0 (Fully active; able to carry on all pre-disease performance without restriction) to 5 (Dead). The baseline ECOG performance status is summarized in the disease-specific baseline characteristics as specified in Section [6.1.4.2](#). A listing of ECOG performance status will be provided.

6.3 Safety Analyses

Safety analyses will be performed separately for Phase 1a Monotherapy Dose Escalation/Exploration, Phase 1b Monotherapy Dose Expansion, Phase 1a Combination Dose Escalation/Exploration and for all patients combined. AEs, clinical laboratory information, vital signs, ECOG performance status, weight, ECGs, and concomitant medications/procedures will be tabulated and summarized for the Safety Population. In addition, the incidence of DLTs in Phase 1a will be summarized using DLT-Evaluable Population. Unless otherwise specified, all analyses will be performed using the Safety Population.

6.3.1 Adverse Event

All AEs were collected from the start of study treatment (Cycle 1 Day 1) through completion of study, at the time points specified in the [Appendix 1](#) and [Appendix 2](#).

6.3.1.1 Adverse Event Dictionary

All AEs will be coded to SOC and PT using Medical Dictionary for Regulatory Activities (MedDRA Version 21.1 or later).

6.3.1.2 Adverse Event Severity

Adverse events will be graded for severity by the investigators using the National Cancer Institute Common Toxicity Criteria for Adverse Events (NCI-CTCAE) Version 4.03. The severity grade of events for which the investigator did not record severity will be categorized as “missing” for tabular summaries and data listings.

- Grade 1: Mild; asymptomatic or mild symptoms; clinical or diagnostic observations only; intervention not indicated; mild AE
- Grade 2: Moderate; minimal, local or non-invasive intervention indicated; limiting age-appropriate instrumental activities of daily living; moderate AE
- Grade 3: Severe or medically significant but non-immediately life-threatening; hospitalization or prolongation of hospitalization indicated; disabling; limiting self-care activities of daily living; severe AE
- Grade 4: Life-threatening consequences; urgent intervention indicated
- Grade 5: Fatal AE

6.3.1.3 Relationship of Adverse Event to Study Drug

A treatment related AE is an AE noted as related to FPT155 or pembrolizumab by the investigator. Events for which the investigator did not record relationship to study drug will be considered related to study drug for summary purposes. However, by-subject data listings will show the relationship as missing.

6.3.1.4 Serious Adverse Events

Serious adverse events (SAEs) will be identified and captured as SAEs if the AEs met the definitions of SAEs that were specified in the study protocol. All SAEs will be collected from the start of study treatment (Cycle 1 Day 1). In addition, any SAE occurring between signing of ICF and start of treatment will be recorded if it is due to a study related procedure. The SAEs will be collected through the Day 100 End of Treatment (EOT) visit.

6.3.1.5 Treatment-Emergent Adverse Events (TEAE)

A treatment-emergent AE (TEAE) is defined as an AE that was not present prior to the start date of study drug or was worsened during treatment and 100 days after last dose of treatment. An AE

that was present at treatment initiation but resolved and then reappeared and the event severity increase while the subject was on treatment is also a TEAE.

6.3.1.6 Summary of Adverse Events and Deaths

An overall summary of TEAEs will summarize the number (%) of patients by the treatment group and overall with: all TEAEs, TEAEs with grade 3 or higher, TEAEs related to FPT155-001, TEAEs related to FPT155-001 with grade 3 or higher, TEAEs leading to study drug discontinuation, serious TEAEs, serious TEAEs related to FPT155-001, TEAEs leading to death. For the Phase 1a Combination Dose Escalation/Exploration, the TEAEs related to pembrolizumab, TEAEs related to pembrolizumab with grade 3 or higher and serious TEAEs related to pembrolizumab will also be included in the overall summary table.

The number and percentage of subjects who experienced at least 1 TEAE will be provided and summarized by SOC, PT, maximum severity, and treatment group. AEs will be summarized in alphabetic order of SOC and then by PT in descending order of total frequency within each SOC. For summaries by severity, the maximum severity will be used for those AEs that occurred more than once in a subject. A subject with multiple adverse events within a SOC is only counted once in this SOC. Similarly, a subject with multiple adverse events within a PT is only counted once in this PT.

- TEAEs
- TEAEs with grade 3 or higher
- TEAEs related to FPT155
- TEAEs related to pembrolizumab (for Phase 1a Combination Dose Escalation/Exploration only)
- TEAEs leading to drug discontinuation of FPT155
- TEAEs leading to drug discontinuation of pembrolizumab (for Phase 1a Combination Dose Escalation/Exploration only)
- Serious TEAEs
- Serious TEAEs related to FPT155
- Serious TEAEs related to pembrolizumab (for Phase 1a Combination Dose Escalation/Exploration only)
- TEAEs leading to death

In addition to the above summary tables, TEAEs will be summarized by PT only in descending order of total frequency.

All AE and recorded deaths for the safety population will be listed.

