#### 4.1.6 Requirements for Archival Tumor Tissue and Fresh Biopsies

Dose Escalation (Monotherapy and FPT155 + pembrolizumab):

- Archival tumor tissue is required. If archival tumor tissue is not available, a fresh biopsy is required prior to treatment for retrospective biomarker analysis.
- Optional pre- and on-treatment biopsies will be requested during screening (prior to treatment) and during treatment (prior to the Cycle 3 Day 1 dose) to explore the relationship between baseline tumor immune phenotype and PD response.
- An additional optional biopsy will be requested at disease progression.

Dose Exploration/Expansion (Monotherapy and FPT155 + pembrolizumab):

- Archival tumor tissue is required for retrospective biomarker analysis. The fresh biopsy required at screening will be accepted in lieu of archival tumor tissue if archival tissue is not available.
- Pre- and on-treatment biopsies will be mandatory during screening (prior to treatment) and during treatment (prior to the Cycle 3 Day 1 dose) to explore the relationship between baseline tumor immune phenotype and PD response.
- An additional optional biopsy will be requested at disease progression.

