#### Type of Patient and Disease Characteristics

- 2.01) Histologically confirmed solid tumors (except primary CNS tumors). For patients enrolled for treatment with FPT155+pembrolizumab: histologically confirmed non-small cell lung cancer not eligible for curative therapy.
- 2.02) For patients in Phase 1a dose escalation (all) and Phase 1a dose exploration (FPT155 monotherapy) only: Disease that is unresectable, locally advanced, or metastatic and has progressed following all standard treatments or is not appropriate for standard treatments.
- 2.03) All patients must have at least one measurable lesion at baseline according to RECIST v1.1. Tumor sites situated in a previously irradiated area, or in an area subjected to other loco-regional therapy, are not considered measurable unless there has been demonstrated progression in the lesion.
- 2.04) Availability of archival tumor tissue and consent to provide archival tumor for retrospective biomarker analysis, or consent to undergo a fresh tumor biopsy during screening
- 2.05) For patients participating in Phase 1a dose exploration cohorts and Phase 1b dose expansion: consent to undergo a mandatory fresh tumor biopsy during screening and on treatment
- 2.06) ECOG performance status of 0 or 1
- 2.07) Life expectancy of at least 3 months in the opinion of the investigator
- 2.08) Willing and able to comply with all study procedures
- 2.09) Prior radiotherapy must be completed at least 2 weeks before first dose of study treatment administration. No radiopharmaceuticals (eg, strontium, samarium) within 8 weeks before first dose of study treatment administration
- 2.10) Prior surgery that requires general anesthesia must be completed at least 14 days before first dose of study treatment administration unless patients have recovered, and it is considered safe after discussion with medical monitor. Surgery requiring local/epidural

anesthesia must be completed at least 72 hours before first dose of study treatment administration and patients must have recovered.

2.11) Screening laboratory values must meet the following criteria:

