#### **5.5 Screen Failures**

Screen failures are defined as patients who consent to participate in the clinical study and enter the screening period but are not subsequently enrolled. A minimal set of screen failure information is required to ensure transparent reporting of screen failure patients to meet the Consolidated Standards of Reporting Trials (CONSORT) publishing requirements and to respond to queries from regulatory authorities. Minimal information includes demography, screen failure details, eligibility criteria, and any SAE.

Individuals who do not meet the criteria for participation in this study (screen failure) may be rescreened after discussion with the Sponsor. Patients who screen fail may repeat screening procedures one time, within the 28-day screening window, inclusive of informed consent. A patient who is rescreened is not required to sign another ICF if the rescreening occurs within the 28-day screening window.

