#### **8.4.1 Time Period and Frequency for Collecting AE and SAE Information**

All SAEs will be collected from the start of study treatment (Cycle 1 Day 1). In addition, any SAE occurring between signing of ICF and start of treatment will be recorded if it is due to a study related procedure. The SAEs will be collected through the Day 100 EOT visit.

All AEs will be collected from the start of study treatment (Cycle 1 Day 1) through completion of study, at the time points specified in the Schedule of Assessments. AEs ascribed to study treatment and SAEs should be assessed through the Day 100 EOT visit.

Medical occurrences that begin before the start of study treatment but after obtaining informed consent will be recorded on the Medical History section of the eCRF, not the AE section, unless they directly correlate to a study-related procedure, in which case they will be reported on the AE eCRF page.

All SAEs will be recorded and reported to the sponsor or designee within 24 hours, as indicated in [Appendix 2](#). The investigator will submit any updated SAE data to the sponsor or designee within 24 hours of it being available.

SAEs occurring after the Day 100 EOT visit should be reported to the Sponsor by the Investigator only if the Investigator considers the event reasonable related to FPT155. SAEs should always be recorded on the AE eCRF.

Investigators are not obligated to actively seek AE or SAE in former study patients. However, if the investigator learns of any SAE, including a death, at any time after a patient has been discharged from the study, and he/she considers the event to be reasonably related to the study treatment or study participation, the investigator must promptly notify the sponsor.

The method of recording, evaluating, and assessing causality of AE and SAE and the procedures for completing and transmitting SAE reports are provided in [Appendix 2](#).

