ADA Sampling		Refer to Protocol Table 4							Blood samples will be collected for ADA analyses at the time points specified and submitted to the central laboratory	

Phase 1b										
Study Phase	Screening	Cycle 1 (21 Days)				Subsequent Cycles* (21 Days)	EOT Follow-Up	LTFU	Notes	
Cycle Day	Screening	D1	D2	D4	D8	D15	D1	28 and 100 Days Post Last Dose		
Window (Days)	-28			± 1	± 1	± 1	± 3	± 7	± 14	
Tumor Tissue Biopsy	X						X	X		In dose exploration and expansion, pre- and on-treatment fresh biopsies will be mandatory at screening (prior to treatment) and prior to the Cycle 3 Day 1 dose, from the same lesion where feasible. An additional optional biopsy will be requested at the Day 28 EOT visit from patients who have documented disease progression.
Study Drug Dosing										FPT155 will be administered over approximately 60 minutes by IV infusion Q3W. Patients may continue receiving study treatment Q3W at the investigator's discretion until any of the protocol-specified treatment discontinuation criteria are met. For FPT155 + pembrolizumab cohorts, pembrolizumab will be administered 30 minutes after completion of the FPT155 IV infusion at a dose of 200 mg by IV infusion. If one study drug is discontinued, the other may be administered for up to 12 months or until protocol-specified discontinuation criteria are met.
Survival Assessment										
Survival Assessment								X		Patients will undergo LTFU for survival by clinic visit or by telephone approximately every 3 months ± 14 days after the Day 28 EOT visit, or until death, loss to follow-up, withdrawal of consent, or study termination by the Sponsor (whichever occurs first).

Abbreviations: ADA = anti-drug antibody; AE = adverse event; CR = complete response; CRS = cytokine release syndrome; CT = computed tomography; DLT = dose limiting toxicity; ECG = electrocardiogram; ECOG = Eastern Cooperative Oncology Group; EOT = end of treatment; IV = intravenous; HBsAG = hepatitis B surface antigen; HCV RNA = hepatitis C virus ribonucleic acid; LTFU = long-term follow-up; MRI = magnetic resonance imaging; PD = pharmacodynamic; PK = pharmacokinetic; PR = partial response; Q3W = every 3 weeks; RECIST = Response Evaluation Criteria in Solid Tumors; WOCBP = women of childbearing potential.

* There is a ± 3-day window for subsequent cycles after Cycle 1

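### Procedure-related events before the first dose are collected, but the SAP tabulates none of them and lists them only for patients who go on to be dosed

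*SAP*

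**What the plan says.** Collection starts before treatment. SAP 6.3.1.4, in the same words as protocol 8.4.1, provides that "any SAE occurring between signing of ICF and start of treatment will be recorded if it is due to a study related procedure". Protocol 8.4.1 sends other medical events between consent and first dose to the medical history page "unless they directly correlate to a study-related procedure, in which case they will be reported on the AE eCRF page". For screen failures, protocol 5.5 sets a minimum data set: "Minimal information includes demography, screen failure details, eligibility criteria, and any SAE".

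Reporting starts with treatment. SAP 6.3.1.5 begins: "A treatment-emergent AE (TEAE) is defined as an AE that was not present prior to the start date of study drug"; it also admits events that worsen on treatment. The overall summary, the ten bulleted tables and the table by preferred term in SAP 6.3.1.6 are all tables of treatment-emergent adverse events (TEAEs). That section closes with the listing rule: "All AE and recorded deaths for the safety population will be listed". SAP 6.3.2 restricts the death listing in the same way. SAP 4.4 defines the Safety Population by receipt of at least part of a dose.

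The study procedure of most interest is the screening biopsy. Protocol 5.1, criterion 2.05, requires patients in exploration and expansion to "consent to undergo a mandatory fresh tumor biopsy during screening and on treatment", and SAP Appendix 2 repeats that "pre- and on-treatment fresh biopsies will be mandatory at screening (prior to treatment"). In dose escalation the rule is softer (protocol 4.1.6): "Optional pre- and on-treatment biopsies will be requested during screening (prior to treatment"), with a fresh biopsy required only if there is no archival tissue.

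**The concern.** The collection rules and the output rules cover different people and different periods. Events that the study chose to record before the first dose fall outside the TEAE definition and so outside every AE table. If the patient is never dosed, they also fall outside the only AE and death listings. A serious or fatal complication of the required screening biopsy in such a patient would be in the database but would not be shown as an event in any planned output.

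The treatment of the two biopsies is also uneven. A new complication of the on-treatment biopsy, taken before Cycle 3 Day 1, can count as a TEAE. The same complication of the screening biopsy cannot. A reader of the tables would see part of the harm from the study's own invasive procedure without being told that the rest is left out.

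**Working it through.** The check is mainly a comparison of rules, followed by a simple sum for scope.

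**Can a pre-dose event enter a table?** Only by worsening after dosing starts (SAP 6.3.1.5). Protocol 8.6.2 requires recovery from acute biopsy effects before dosing, so for biopsy complications this route is nearly closed. The opening of SAP 6.3 speaks of tabulating AEs rather than TEAEs, and protocol Table 12 speaks of treated patients with AEs. SAP 6.3.1.6, which names the actual tables, narrows this to TEAEs, and both general statements cover dosed patients only.

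**Does the general listing rule help?** SAP section 5 makes enrolled patients the default for listings, but the default yields where another population is named, and SAP 6.3.1.6 and 6.3.2 name one. Even the default would miss screen failures, who by protocol 5.5 are never enrolled.

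**Deaths.** The deaths summary in SAP 6.3.2 names no population, so the default in SAP 6.3, the Safety Population, applies. A death before dosing enters neither the summary nor the listing.

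**Disposition.** SAP 6.1 and 6.1.1 use the Enrolled Population and give reasons for discontinuation. Protocol 7.2 includes AE and death among the reasons for leaving the study.

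For a procedure-related event with onset between consent and first dose:

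| Patient | AE table | AE and death listing | Disposition output |
|---|---|---|---|
| Later dosed | No, unless it worsens on treatment | Yes | Not as an event |
| Enrolled, never dosed | No | No | Reason for leaving only |
| Screen failure | No | No | No |

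**Scope of the mandatory biopsy.** Planned numbers, from the protocol synopsis (Number of Patients): monotherapy escalation 58, monotherapy exploration 50, expansion 240, combination escalation 30, combination exploration 30.

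- Total: 58 + 50 + 240 + 30 + 30 = 408, which agrees with the plan.
- Parts with a mandatory screening biopsy: 50 + 240 + 30 = 320, and 320 / 408 = 78%.
- The 240 is a ceiling for eight cohorts. Appendix 11 of the protocol defines five, giving 5 × 30 = 150 and 50 + 150 + 30 = 230.

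Protocol 8.6.2 accepts a standard-of-care biopsy taken within 28 days before Cycle 1 Day 1 if the sample is suitable, so fewer patients than this would have a study-performed biopsy. Biopsied screen failures would add to the number. The documents quantify neither adjustment.

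**The case against.** The SAP carries out the protocol here. Protocol 9.4.2 puts all safety analyses on the Safety Population, and the primary safety objectives concern FPT155, alone or with pembrolizumab, not the biopsy. TEAE tables in treated patients are the usual answer to those objectives. This stands as an explanation of the tables. It does not explain why events that were deliberately collected should be left out of a listing.

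Several stronger readings are tempting, and the documents do not support them:

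- A reader might infer that a patient with a serious pre-dose complication appears nowhere. That is true of screen failures. An enrolled, undosed patient still appears in the disposition outputs by reason, and a dosed patient's pre-dose event is listed.
- A reader might infer that safety oversight is weakened. Protocol 8.4.1 sends SAEs to the sponsor within 24 hours, so the loss is in what the study report displays.
- A reader might multiply 320 by an assumed complication rate to count lost events. No rate is given, the product would include events in dosed patients (which are listed), and the number of undosed patients is unknown.
- A reader might infer that the rule systematically removes the worst cases. That is plausible, but not shown: patients who recover can be dosed and are then listed, and protocol 5.5 allows one rescreen within the 28-day window.
- A reader might infer that the trial can say nothing about biopsy risk. New events after the on-treatment biopsy are tabulated as TEAEs, though not separated by cause.

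**Conclusion.** The point holds as a reporting gap. Pre-dose procedure-related events in dosed patients are listed but not tabulated. In never-dosed patients they are neither tabulated nor listed as events, and the same applies to any SAE recorded in a screen failure. The mandatory screening biopsy makes this more than a formality: it applies in parts planned for up to about 320 patients (about 230 on the five expansion cohorts now defined), before subtracting acceptable standard-of-care biopsies and adding biopsied screen failures.

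The number of omitted events cannot be estimated from the documents. No endpoint, TEAE rate or dose decision changes. The conclusion assumes that the population named in SAP 6.3.1.6 and 6.3.2 overrides the general listing default, which is how SAP section 5 is worded. It is worth correcting because a stated rule drops harms already collected and the remedy is cheap.

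**What to change.** In SAP 6.3.1.6 and 6.3.2, change the population for the AE, SAE and death listings from the Safety Population to all consented patients with a recorded event, naming screen failures and enrolled-but-undosed patients explicitly. Flag onset before first dose and, where recorded, relation to a study procedure.

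Add one line of counts: patients with a pre-dose procedure-related SAE, split by dosed and not dosed. Do not turn this into a biopsy-risk percentage unless the number of screening biopsies performed is available. The minimum screen-failure data in protocol 5.5 do not include whether a biopsy was done, or non-serious events, and an all-procedure numerator over a biopsy denominator would not measure biopsy risk in any case.

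State in the SAP that these outputs are an exception to the Safety Population rule in protocol 9.4.2. The TEAE tables stay as they are. The cost is that stated exception and a small amount of extra programming; the listing and the count use events already recorded.

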6.3.1.7 Dose-Limiting Toxicity

The summary and listing of DLTs will be performed on the DLT-Evaluable Analysis Set. A summary of DLT will be provided by SOC, PT, and severity. The DLTs will also be summarized by PT only in descending order of total frequency. All DLTs will be listed.

6.3.2 Deaths

All deaths during the study, deaths within 28 days after the last dose of treatment, deaths within 100 days after the last dose of treatment and deaths beyond 100 days after the last dose of treatment will be summarized, the cause of deaths will also be included. All recorded deaths for safety population will be listed.

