#### 4.2 Study Treatment and Duration

FPT155 will be administered Q3W over approximately 60 minutes by IV infusion.

In combination with FPT155 and pembrolizumab, pembrolizumab will be administered a minimum of 30 minutes following completion of the FPT155 infusion. Pembrolizumab should be administered per the pembrolizumab Product Information.

Treatment is administered Q3W until disease progression, unacceptable toxicity, or patient withdrawal. If one drug is discontinued, treatment may continue with the other alone for up to an additional 12 months. Treatment beyond disease progression may be allowed in patients with initial RECIST v1.1 defined progressive disease if the criteria in Section 4.3 are met.

Patients should have end of treatment (EOT) follow-up visits approximately 28 days and 100 days after the last dose of treatment on study. In addition, patients enrolled in dose expansion will be followed for survival.

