#### 4.4 End of Study Definition

The EOT follow-up visit approximately 100 days after the last dose of treatment on study will be considered the end of the study in Phase 1a.

In the Phase 1b portion of the study, patients will also be followed for survival by clinic visit or by telephone approximately every 3 months after the Day 100 EOT visit. Death, loss to follow-up, or withdrawal of consent of the last study subject, or study termination by the Sponsor (whichever occurs first), will be considered the end of the study in Phase 1b.

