### 8.1 Efficacy Assessments

#### 8.1.1 Tumor Assessment for the Study

Tumor assessments consist of clinical examination and appropriate imaging techniques (preferably CT scans with appropriate slice thickness per RECIST v 1.1; MRI is acceptable). Assessments should be performed as outlined in the Schedule of Assessments. The same methods used to detect lesions at baseline are to be used to follow the same lesions throughout the clinical study.

Tumor response assessment will be performed by the investigator per RECIST v 1.1 guidelines ([Eisenhauer 2009](#)).

Tumor assessments will be performed at screening, then every 6 weeks from the first dose for 24 weeks, and then every 12 weeks thereafter. Once an initial CR or PR is reported by the investigator, confirmatory scans must be performed 4–6 weeks later.

If patient terminates study treatment prior to scheduled CT/MRI scans, patient should have scans done at the EOT visits (does not need to be repeated if performed within 8 weeks prior to the end of treatment visits, or if tumor progression was previously determined).

After discontinuation of study treatment for reasons other than progressive disease, withdrawal of consent, or initiation of additional anti-cancer therapy, tumor assessments will continue every 12 weeks until disease progression, withdrawal of consent or start of new anti-cancer therapy.

In the Phase 1b portion of the study, patients in LTFU for survival must have tumor scans every 12 weeks if tumor progression was not previously determined and/or use of alternative anti-cancer therapy has not been initiated.

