6.2.5 Efficacy Endpoint: OS

Overall Survival (OS), defined as the time from the first dose of study treatment until death from any cause.

OS in months will be calculated as: (date of death from any cause - date of first dose + 1)/30.4375. Patients who are known alive as of their last known status will be censored at the date

of their last known to be alive. OS for patients will be summarized using 25th, 50th (median), and 75th percentiles with associated 2-sided 90% CIs, as well as percentage of censored observations. The median will be estimated by using the Kaplan-Meier method and corresponding 2-sided 90% CI using Brookmeyer and Crowley methodology (using log-log transformation). Number and percent of survival subject at 1 year will be estimated. The detailed censoring rules are displayed in [Table 11](#).

Table 11 Censoring Rules for OS

Situation	Outcome	Date of Progression or Censoring	Event Description/ Censoring Reason
Death before data cutoff	Event	Date of death	Death
Death after data cutoff	Censored	Date of data cutoff	Alive on or before data cutoff
No death before data cutoff	Censored	Date subject last known to be alive	Alive on or before data cutoff
Discontinued from study without death prior to data cutoff	Censored	Date subject last known to be alive	Discontinued from study

By-subject listings will be provided for target lesion, nontarget lesion, new lesion, and tumor response assessment. A by-subject listing of subsequent anti-cancer treatment will also be provided. By-subject listings for the efficacy endpoints above will also be provided.

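### The SAP's pooled figure for deaths beyond 100 days after last dose mixes Phase 1b patients followed for survival with Phase 1a patients whose study ends at about Day 100

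*SAP*

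**What the plan says.** **Death summary.** SAP 6.3.2 groups deaths by time since last dose and includes the late category: "deaths within 100 days after the last dose of treatment and deaths beyond 100 days after the last dose of treatment will be summarized". The section names no phase. SAP 6.3, which governs it, runs safety analyses for Phase 1a monotherapy, Phase 1b, "Phase 1a Combination Dose Escalation/Exploration and for all patients combined". SAP section 5 summarises categorical variables by number and percentage.

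**Follow-up.** Protocol 4.4 says that the visit "approximately 100 days after the last dose of treatment on study will be considered the end of the study in Phase 1a". The same section continues: "In the Phase 1b portion of the study, patients will also be followed for survival by clinic visit or by telephone". Protocol 4.2 agrees: "In addition, patients enrolled in dose expansion will be followed for survival". Under protocol 8.4.1, after the Day 100 visit SAEs reach the sponsor only if the investigator considers them reasonably related, and sites need not look actively for events in former patients.

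**Passages that do not fit.**
- Protocol Table 2 covers dose exploration as well as expansion. Its survival row carries no Phase 1b limit, although the text at the head of the table does limit long-term follow-up to Phase 1b.
- Protocol 8.1.1 says that, for patients who stop treatment without progression, "tumor assessments will continue every 12 weeks until disease progression, withdrawal of consent or start of new anti-cancer therapy", with no phase limit. SAP Appendix 1, the Phase 1a dose escalation schedule, repeats that rule while placing the end of Phase 1a at Day 100.

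**The concern.** A count of deaths beyond Day 100 has meaning only for patients in whom such deaths would be found. A Phase 1a patient who dies of cancer on, say, day 130 after the last dose has in general no scheduled route into the database, yet stays in the denominator. Two displays suffer: the Phase 1a late-death row, which will look low because it was not systematically collected, and the pooled column, which averages followed and unfollowed patients. In a first-in-human study deaths are a core safety table, and nothing in the plan warns the reader that a small number there may come from the follow-up schedule.

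**Working it through.** **Inputs.** Planned numbers from SAP 2.3 and protocol 9.2: monotherapy escalation 58, monotherapy exploration 50, combination escalation 30, combination exploration 30, Phase 1b 8 × 30 = 240. Planned numbers stand in for the eventual Safety Population.

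**Step 1, the plan's own total.** 58 + 50 + 30 + 30 + 240 = 408, as stated.

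**Step 2, share without survival follow-up under protocol 4.2 and 4.4.** Phase 1a is 58 + 50 + 30 + 30 = 168, and 168/408 = 41.2%. Phase 1b is 240/408 = 58.8%.

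**Step 3, dilution.** Let q be the proportion of followed patients with a recorded death beyond Day 100, and F the number followed. If unfollowed patients contribute none, the pooled proportion is q × F/408. The values of q are assumptions, because the documents give none.

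| Assumed q | F = 240 (Phase 1b only), factor 0.588 | F = 320 (exploration also followed), factor 0.784 |
|---|---|---|
| 20% | 11.8% | 15.7% |
| 40% | 23.5% | 31.4% |
| 60% | 35.3% | 47.1% |

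The last column takes the Table 2 survival row at its word for the 50 + 30 = 80 exploration patients and gives them the same q: F = 240 + 80 = 320. The unfollowed are then the 58 + 30 = 88 escalation patients, 88/408 = 21.6%.

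**Step 4, is the late period important?** Assume exponential survival after last dose with median m months. The share of deaths falling after Day 100 is 2^(−100/(30.4375 × m)).

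- m = 3: 46.8%
- m = 6: 68.4%
- m = 9: 77.6%
- m = 12: 82.7%

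These medians are illustrative. The shares are upper limits on what Phase 1a would miss, since some late deaths may still be reported. The +7-day visit window alone would recover only 1.1 to 2.4 percentage points.

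**The case against.** The strongest reply is that the plan also reports each part separately, so an undiluted Phase 1b row will exist, the study is wholly descriptive, and no dose decision is shown to rest on the pooled column. That limits the harm but does not remove it: the Phase 1a row is itself open to misreading, and no note about follow-up is planned.

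A reader might infer that Phase 1a late deaths must be practically nil by design. The documents do not support that. The Table 2 survival row may bring exploration patients into survival follow-up, scans continue every 12 weeks in patients who stop without progression, and related serious events stay reportable after Day 100. The accurate statement is that collection is not systematic. It is weakest in escalation and uncertain in exploration.

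A reader might also infer that Phase 1a overall survival will be estimated with informative censoring at last dose plus 100 days, because SAP 6.2.5 names no phase and adds that "Number and percent of survival subject at 1 year will be estimated". This cannot be established. SAP 6.2 assigns endpoints to phases through Table 9, whose exploratory cells are redacted, and the visible Phase 1a monotherapy efficacy list in protocol section 3.0 has response rate, duration of response and PFS but not survival. The hidden text may already confine OS to Phase 1b.

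Finally, removing late Phase 1a deaths from the tables altogether could leave a reportable related death visible only in a listing. That objection stands and shapes the remedy.

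**Conclusion.** The point holds for the late-death summary. As written, up to 41.2% of the pooled denominator has no systematic follow-up in the period counted, and the pooled percentage would be about 0.588 times the Phase 1b value. If exploration patients are followed, the figures are 21.6% and 0.784. Both factors assume planned enrolment and no recorded late deaths among unfollowed patients. Any late death that is captured moves the pooled figure up, so they describe the largest dilution under each reading. The by-part tables contain the damage, but a low Phase 1a or pooled number should not be read as few deaths. No conclusion is drawn about overall survival in Phase 1a.

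**What to change.** **SAP 6.3.2.** Compute the percentage of deaths beyond 100 days only among patients under protocol survival follow-up (Phase 1b as protocol 4.2 and 4.4 stand), and give no pooled percentage. Show any Phase 1a death reported after Day 100 as a count, with a footnote that Phase 1a is not systematically followed past Day 100. This keeps late related deaths visible in the tables.

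**Reconcile the follow-up passages.**
- Bring the protocol Table 2 survival row into line with the text at the head of that table and with sections 4.2 and 4.4, so that it is clear whether exploration patients are followed for survival. If they are, they join the denominator. The starting point also needs one answer: the Table 2 header and SAP Appendix 2 count from the Day 28 visit, while protocol 4.4 and the Table 2 survival row count from Day 100.
- Reconcile the Phase 1a end of study in protocol 4.4 with the off-treatment scans in protocol 8.1.1 and SAP Appendix 1. SAP 6.2.1 lets best overall response run to the end of study at the latest, so the end date can affect which scans count.

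**Cost.** SAP wording, one table footnote and a protocol clarification. The SAP change needs no new data collection. What is lost is a single pooled late-death percentage, which would not be interpretable in any case.
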